Study Protocol

Personalized Booster Feedback After Alcohol Health Education

NCT03440476

6/23/2022

Principal Investigator:

[name].

Description and Purpose of the Project

Heavy episodic alcohol use within the college student population is widespread, creating problems for student drinkers, their peers, and their institutions. Negative consequences from heavy alcohol use can be mild (e.g., hangovers, missed classes), to severe (e.g., assault, even death). Although online interventions targeting college student drinking reduce alcohol consumption and associated problems, they are not as effective as in-person interventions. Online interventions are cost-effective, offer privacy, reduce stigma, and may reach individuals who would otherwise not receive treatment. In a recently completed randomized, controlled trial, an emailed booster with personalized feedback improved the efficacy of a popular online intervention (Braitman & Henson, 2016). Although promising, the booster incorporated in the study needs further empirical refinement.

The current project seeks to build on past progress by further developing and refining the booster. In particular, one aspect missing from online interventions is a connection with a person invested in improving the student's outcomes. The current study aims to generate a personal connection for online interventions through a follow-up booster emailed by a member of the research staff. Outcomes will be compared for participants who receive a follow-up booster with similar content, but is clearly automatically generated and not from any particular individual.

There are 3 conditions: all participants receive the initial online intervention targeting college drinking. Condition 1 (the control group) receives an email with a reminder to complete the follow-up surveys, but no feedback (i.e., no booster). Condition 2 receives an emailed booster with normative feedback plus protective strategies feedback, clearly automatically generated. Condition 3 receives an emailed booster with normative feedback plus protective strategies feedback, from a member of the research staff. The booster content alone (automatically generated) may be efficacious, or the additional personal connection may enhance the effect.

Primary Aims

The aim of the current study is to examine if personal contact enhances the tailored feedback received via booster email.

Participants

Eligible participants must be 1) a current college student at the sponsor institution at the time of enrollment; 2) between the ages of 18 and 24; and 3) consumed at least one standard drink of alcohol in the past 2 weeks. Power analyses were conducted using Monte Carlo simulation methods within Mplus (version 5.21, Muthén & Muthén). Effect sizes, variance, and covariances used were based on data from a preliminary study with similar eligibility criteria using the same booster content (Braitman & Henson, 2016). We estimated a retention rate of 76%, the average reported in a meta-analysis of RCTs assessing alcohol interventions for first-year college students (Scott-Sheldon et al., 2014). Monte Carlo simulation methods indicated that for the effect size expected ($b = 6.57$, $\beta = 0.537$) and for the expected 24% attrition, a sample size of $N = 180$ total students should yield power = .813 to detect the booster effects.

Recruitment Procedure

Recruitment uses two methods. 1) An advertisement is placed in the Announcement system at the host institution, which includes a link to a screener survey. 2) An email describing the study is sent to undergraduate students who meet the age eligibility criteria (18-24 years old) at the sponsoring institution who attend classes on the main campus of the sponsoring institution, which also includes a link to a screener survey. In addition to the assessing eligibility criteria (age, student status, and alcohol consumed) additional irrelevant questions are included in the screener survey to discourage ineligible participants from re-taking the screener survey with different answers. Students who screen as eligible are invited to provide their contact information (name, email, and phone number), and to schedule their participation in the baseline session via Calendly).

Study Procedure

Emerging adult college drinkers are recruited as described above. After completing the screener to verify eligibility, participants schedule their baseline session. After completing baseline, they are invited to complete two follow-up surveys 1 and 3 months after their baseline session. Participants receive a \$20 gift card for their participation (from Amazon or Target) for baseline participation. Additionally, participants receive \$10 for each completed follow-up survey (for the 1-, 3-month assessments). As an additional incentive, participants who complete all assessments are given a \$10 bonus (yielding \$50 total for the study).

Baseline: Upon arrival at the research lab, participants are provided with the informed consent document, and have the opportunity to ask questions. After consenting to participate, they are directed to one of the computers in the lab. Because data are collected in a computer lab setting, each computer has a privacy partition (behind and beside the monitor). This is to minimize the possibility of participants viewing each other's screens. Additionally, participants are provided with headphones to minimize disruption from the other computers. All participants complete a computerized survey at the beginning of their first appointment that assesses alcohol use, alcohol-related problems, protective behavioral strategies for drinking and their perceived effectiveness, motives and expectancies for alcohol use, anonymized social network characteristics, context of their most recent drinking occasion, marijuana and tobacco use, and demographics measures. Upon beginning the survey, participants are randomly assigned within the survey system to one of the three study conditions: neutral email (no feedback), auto-generated booster email (feedback, no warmth), warm booster email (feedback written by a person using warm, personable language). After completing the initial assessment, participants are then directed to navigate through the *eCHECKUP TO GO for Alcohol* program (San Diego State University Research Foundation, 2018) until it is completed (approximately 20-30 minutes).

Follow up assessments: Approximately one and three months after the initial assessment, researchers send each participant an email reminding them to complete the follow-up assessment in exchange for payment. This email includes a link to an online follow-up survey that assesses alcohol use, related problems, protective behavioral strategies for drinking and their perceived effectiveness, anonymized social network characteristics, context of their most recent drinking occasion, and marijuana and tobacco use.

Boosters: Approximately two weeks after the intervention, all participants receive an additional email from the researcher. Information in the emails for the experimental booster groups serve as a booster to the original intervention. Baseline data are used to provide students with normative information (e.g., typical drinking among ODU students who are male/female

depending on the gender of the recipient), and reminders of protective behavioral strategies they can use to reduce drinking-related harm. In the auto-generated booster email condition, the feedback is delivered neutrally: “Hello, This feedback has been automatically generated for Carlton based on your answers to the online survey you completed in the research lab for the Project ‘Personalized Booster Feedback after Alcohol Health Education’”), whereas in the warm booster email condition, the feedback is delivered by a person using warm, personable language (i.e., Dear Carlton, My name is [name] and I’m your personal research coordinator for the Project ‘Personalized Booster Feedback after Alcohol Health Education’. I track your responses over the course of the study, and I’m writing to give you feedback about your answers to the online survey you completed in the research lab”). Participants in the control condition receive an email with no feedback.

Measures

The same measures are included in baseline and the follow-up surveys:

Participants’ **alcohol use** is assessed using a modified version of the Daily Drinking Questionnaire for the past 30 days (Collins et al., 1985). Additionally, participants describe specific aspects regarding their drinking in the past 30 days (e.g., highest consumption in a single day). **Descriptive Norms** are assessed by modifying the DDQ to reflect their expectations for typical male students at the same institution, typical female students at the same institution, and close friends. Injunctive Norms are assessed using 10 items (Carey et al., 2010). **Alcohol-related problems** are assessed using the 48-item Young Adult Alcohol Consequences Questionnaire (YAAQ; Read et al., 2006), modified to assess the past 30 days rather than the past year. **Protective behavioral strategy** (PBS) use is assessed using Sugarman and Carey’s (2007) Strategy Questionnaire (SQ). **Perceived effectiveness of PBS** is assessed by modifying the instructions and response scale for Sugarman and Carey’s (2007) measure to assess how effective participants perceive each strategy to be. **Importance of PBS** use for all people and self are assessed with 10 items created by the researcher. **Alcohol expectancies** are assessed using the Comprehensive Effects of Alcohol questionnaire (CEOA; Fromme et al., 1993). **Motives for alcohol use** are assessed using the Drinking Motives Questionnaire (DMQ; Cooper, 1994). **Alcohol beliefs** about how salient alcohol use is to college life are assessed using the College Life Alcohol Salience Scale (CLASS; Osberg et al., 2010). **Social network** and affiliated characteristics are assessed using the adapted version (DeMartini et al., 2013) of the Brief Important People Interview (BIP; Zywiak et al., 2002). Participants are asked to report characteristics and context for their **most recent drinking occasion**. This assessment is a collection of items mostly created by the researcher, but incorporates a modified version of the **Alcohol Offers** scale (Read et al., 2005), and a truncated, occasion-specific version of **drinking motives** (Cooper, 1994). **Marijuana use** is assessed similar to prior research (e.g., Collins et al., 2014), and **tobacco use** is assessed using items created by the researcher. **Demographics and general information** are collected during the initial assessment only; participants report their age, race, sex, Greek affiliation (i.e., membership in fraternities or sororities), GPA, class standing, athletic status student status (full- versus part-time), residential status, relationship status, sexual identity, height, and weight (for blood alcohol content calculations).

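### As described, only the control arm's two-week email carries a survey reminder, so comparisons with control may differ by one early prompt as well as by feedback; a small, cheaply removed ambiguity

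*Protocol*

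**What the plan says.** The arms are defined in the Protocol under Description and Purpose of the Project. For control: "Condition 1 (the control group) receives an email with a reminder to complete the follow-up surveys, but no feedback (i.e., no booster". For the automated arm: "Condition 2 receives an emailed booster with normative feedback plus protective strategies feedback, clearly automatically generated". For the staff arm: "Condition 3 receives an emailed booster with normative feedback plus protective strategies feedback, from a member of the research staff". A survey reminder is named in the first definition and in neither of the others.

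Under Study Procedure, the Boosters paragraph gives the timing: "Approximately two weeks after the intervention, all participants receive an additional email from the researcher". It describes the booster emails as normative information plus protective-strategy reminders and quotes only their opening lines. On control it adds: "Participants in the control condition receive an email with no feedback". That sentence does not mention the survey reminder.

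The Follow up assessments paragraph sets a reminder, tied to payment, for everyone: "Approximately one and three months after the initial assessment, researchers send each participant an email reminding them to complete the follow-up assessment in exchange for". The survey link comes with that later email. Payments are also the same in all arms: \$10 per follow-up survey and a \$10 bonus for completing all assessments.

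On expected loss, the Participants section says "We estimated a retention rate of 76" percent, a single overall rate.

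**The concern.** Comparing a booster arm with control is meant to show what the feedback adds. If the control email is a survey reminder and the booster emails contain none, the arms differ in two ways: feedback, and a prompt to return the survey.

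The second difference matters because follow-up outcomes come only from returned online surveys and 24% loss is expected. A prompt given to one arm can change how many people answer in that arm, and who they are. If people who do not answer drink differently from those who do, part of an observed booster-versus-control difference would reflect who responded. Unequal follow-up between arms also leaves a booster claim open to challenge, whatever the size of the bias.

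**Working it through.** **1. The plan's own figure.** The Participants section gives power .813 for N = 180, b = 6.57, β = 0.537 and 24% attrition, from an Mplus simulation. The model, variances, alpha and allocation are not stated, so it cannot be rebuilt. As a rough proxy, take β as a standardized mean difference, 60 per arm, 45.6 retained per arm and alpha 0.05. Power is then 0.727 for one booster arm against control (two-sided), 0.842 for both boosters pooled against control (two-sided), and 0.821 for a single pair tested one-sided. This neither confirms nor refutes .813, and the present point does not depend on it.

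**2. The two-week emails side by side, as described.**

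| Arm | Feedback | Survey reminder |
|---|---|---|
| Condition 1 (control) | No | Stated |
| Condition 2 (automated) | Yes | Not mentioned, not excluded |
| Condition 3 (staff) | Yes | Not mentioned, not excluded |

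Conditions 2 and 3 match on the reminder. Conditions 1 and 2, and 1 and 3, do not match as written.

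**3. Scale in participants.** Assuming equal allocation, 180 / 3 = 60 per arm, and 60 × 0.76 = 45.6 expected responders. A retention shift of 5 to 15 points (assumed) is 0.05 × 60 = 3 to 0.15 × 60 = 9 participants in an arm.

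**4. Bias formula.** Let a be the fraction lost in an arm, and let non-responders have a mean d SD above responders, with the same d in each arm. The full-arm mean is the responder mean plus a × d, so the responder mean is too low by a × d. The completers-only difference between two arms is therefore biased by (a1 − a2) × d in absolute size.

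**5. Results.** The retention gap and d are assumptions. The percentage column also assumes that β = 0.537 is a standardized mean difference, which the protocol does not say.

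| Retention gap | Bias, d = 0.25 | Bias, d = 0.5 | Share of 0.537 (d = 0.25; d = 0.5) |
|---|---|---|---|
| 5 points | 0.0125 SD | 0.025 SD | 2.3%; 4.7% |
| 10 points | 0.025 SD | 0.05 SD | 4.7%; 9.3% |
| 15 points | 0.0375 SD | 0.075 SD | 7.0%; 14.0% |
| 20 points | 0.05 SD | 0.10 SD | 9.3%; 18.6% |

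**6. Effect on power.** Hold overall retention at 76% and let control exceed each booster arm by 0 to 20 points. Completers (control / each booster) then run from 45.6 / 45.6 to 53.6 / 41.6. Proxy two-sided power for one pair stays between 0.727 and 0.739. Unequal numbers alone hardly matter; the issue is who responds.

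**The case against.** The strongest reply is that this rests on silence. The arm definitions are one sentence each and name what distinguishes the arm. No sentence says the booster emails omit a reminder, and only their openings are quoted. The control wording also fits a common email with the feedback removed. This stands: the content of the booster emails is not known. It does not dispose of the point, because an element shared by all arms should not be listed in one definition only. Either the definitions are incomplete or the emails differ.

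Second, the main retention measures are common to all arms: one two-week email each, the same 1- and 3-month reminders with the link, and the same payments. This stands. A reader might infer that control alone is prompted to respond, but the documents do not support that. The most that can differ is one early mention.

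Third, a reader might infer that the trial's main question is confounded. It is not: the Primary Aims section asks whether personal contact adds to the feedback, which is Condition 3 versus 2, and those descriptions match on the reminder. Comparisons with control still matter. The protocol raises the possibility that the automated booster works by itself, and its power statement refers to booster effects.

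Fourth, the direction is unknown. The quoted openings of both booster emails mention the project and the completed survey, and the staff version says responses are tracked through the study. These too could encourage return. This stands.

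Finally, the bias figures assume a completers-only comparison, and missing-data handling may be set out in a statistical analysis plan that is not at hand.

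**Conclusion.** The point holds in a limited form. The reminder is listed for the control email alone, so a team following the text would give control one extra survey prompt about two weeks before the 1-month survey. Only contrasts with control are exposed.

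Differential attrition is possible but not shown: the protocol gives no retention by arm. With a 5- to 15-point gap and d = 0.5 SD, the bias is about 0.03 to 0.08 SD, or roughly 5% to 14% of 0.537. That range depends on the assumed gap and d, a completers-only comparison and, for the percentages, reading β as a standardized difference. If the prompt raised control retention and non-responders drank more, the error would favour the boosters; reversing one of those conditions would reverse the sign. A reader might take this as established confounding of retention with arm, but the text supports only a possible imbalance of one prompt. Minor.

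**What to change.** Put one identical sentence reminding participants of the follow-up surveys in all three two-week emails. In Description and Purpose of the Project, define Condition 1 as the same email without feedback. On the survey prompt, the arms are then matched.

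If the booster emails already contain the reminder, only the arm definitions need correcting. If emails have already been sent, state what each contained and report retention by arm at 1 and 3 months.

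The cost is at most one added sentence in each booster email and a short edit to the protocol, with no extra contacts, staff or participants.

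### Does randomizing when the baseline survey is opened, rather than at the end of the lab session, damage the comparison of the three arms?

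*Protocol*

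**What the plan says.** The protocol fixes this order under Study Procedure:

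- **Baseline.** After consent, "Upon beginning the survey, participants are randomly assigned within the survey system to one of the three study conditions". The rest of the survey follows, then the online alcohol program, which takes about 20 to 30 minutes. Both are the same for everyone.
- **Boosters.** "Approximately two weeks after the intervention, all participants receive an additional email". This is the first point at which the arms differ. For the two booster arms, "Baseline data are used to provide students with normative information", which depends on the recipient's gender. The automated email is described as "based on your answers to the online survey you completed in the research lab", and the warm email sets out to "give you feedback about your answers to the online survey you completed in the research lab". By contrast, "Participants in the control condition receive an email with no feedback".
- **Follow-up.** The opening paragraph of Study Procedure invites participants to the 1- and 3-month surveys once they have completed baseline.

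Under Measures, past-30-day drinking comes from the survey's modified Daily Drinking Questionnaire, and demographics "are collected during the initial assessment only; participants report their age, race, sex" among other items. Before the survey only the screener exists. Recruitment Procedure says it covers age, student status and alcohol consumed, with some further questions added to hide the eligibility criteria.

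**The concern.** Randomization is usually best placed as close as possible to the point where treatment diverges. Here it comes a full lab session and about two weeks earlier, and the document shows no benefit from that. Two consequences suggest themselves.

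1. Someone who opens the survey and stops has been randomized. That person could still be sent the control email in full, but not a fully tailored booster, because its content comes from the survey answers. Keeping such people would dilute the booster arms against control. Removing them would be an exclusion after randomization.
2. At the moment of assignment neither sex nor survey-measured drinking is recorded, so the randomization cannot be stratified on them. With about 60 per arm, a chance imbalance in baseline drinking is quite possible.

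If these mattered, the booster-versus-control contrasts would be weakened, and the warm-versus-automated contrast named under Primary Aims would lose some sensitivity. Assigning from a closing survey page at the end of the same session would seem to avoid both at little cost.

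**Working it through.** **Inputs.** From Participants: N = 180, 24% attrition, standardized effect 0.537, power .813. Assumed, because the document does not state them: equal arms of 60, the share of starters who do not finish, the correlation of a screener drinking item with survey drinking, and the shape of the drinking distribution.

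**The plan's power figure.** After attrition, 60 × 0.76 = 45.6 per arm. A pairwise two-sided 5% test gives Φ(0.537/√(2/45.6) − 1.96) = Φ(0.604) = .727. One-sided at 5% gives Φ(2.564 − 1.645) = .821. The pooled boosters against control, two-sided, give .842. The contrast, the level and the sidedness behind .813 are not stated, so the figure is neither confirmed nor refuted. Nothing below depends on it.

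**Can non-finishers bias the comparison?** The survey and the program are common to all arms, and the first arm-specific event is the email. Stopping during the session is therefore unrelated to the treatment received. Leaving non-finishers out of all three arms gives a comparison as unbiased as assignment at completion.

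**Can they dilute it?** Only if they supply follow-up outcomes. Study Procedure places the follow-up invitation after completed baseline, with no distinction by arm. Read that way, a mid-survey quitter has no outcome in any arm. Someone who stops later, during the online program, has already given the survey answers that a booster needs.

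**How many could there be?** The protocol describes none. Baseline is one supervised session with a $20 gift card, and its wording takes completion of the survey and the program for granted.

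**Would later assignment save recruitment?** Starters needed for 180 finishers, and finishers per 180 starters:

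| Not finishing (assumed) | Starters for 180 finishers | Finishers from 180 starters |
|---|---|---|
| 2% | 180/0.98 = 184 | 176.4 |
| 5% | 180/0.95 = 190 | 171 |
| 10% | 180/0.90 = 200 | 162 |

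The same starters give the same finishers under either rule. If recruitment stopped at 180 randomized and 5% did not finish, on top of the 24%, the pairwise two-sided power would be .705 instead of .727. That follows from enrolling fewer finishers and not from the moment of assignment; 190 starters restore it. The 76% retention may also already count such losses.

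**What would stratification add?** Chance that two arms of 60 differ by more than 0.25 SD in baseline drinking:

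- No stratum: 2 × (1 − Φ(0.25/√(2/60))) = 2 × (1 − Φ(1.37)) = .171.
- Median split on survey drinking, normal: unexplained variance 1 − 2/π = .363, giving .023. Exponential: 1 − (ln 2)² = .520, giving .057. Simulation with blocks of 6 gave .026 and .060.
- Screener item as stratum, simulated: .138 to .145 for a correlation of 0.5, and .099 to .118 for 0.7.

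The gain over a screener stratum is thus 10-15% against 3-6%. Measures says the same instruments are used at baseline and follow-up, so baseline drinking can enter the model. The mean variance inflation of the adjusted contrast is then 1.009 without strata, 1.006 to 1.008 with a screener stratum and 1.003 to 1.004 with a survey stratum. The largest difference is 1.009 − 1.003 = 0.006, that is, 0.6%. Sex could be asked in the screener, which already carries extra questions, without moving the assignment.

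**The case for a change.** The strongest case for a change is that it is cheap. One sentence and a closing survey page would ensure that everyone randomized has the data their email needs, and that the randomized set matches those invited to follow-up. The follow-up rule can also be read more broadly: the paragraph on follow-up assessments speaks of reminding every participant. On that reading a mid-survey quitter could be followed up, and each one would shrink a booster arm's effect against control by at most 1/60 = 1.7% (3 people: 5%; 6 people: 10%). If 5% were kept and answered follow-up as often as others, pairwise two-sided power would fall from .727 to Φ(0.95 × 2.564 − 1.96) = .683.

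The order of events and this arithmetic are correct. But the broader reading sets aside the rule stated earlier in the same section, and every rate is assumed for a single paid visit. Even then, leaving non-finishers out of all arms alike removes the dilution without selection.

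Nor is the change free of risk. Participants would have to leave an external program and open a further survey page; anyone who finished both tasks but missed that page would never be assigned. The present rule has no such gap. Whether the survey system can run stratified blocks is not known from the document.

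**Conclusion.** The concern does not hold. Assignment inside the survey system at the start of baseline is a valid randomization, and a sponsor who follows the plan as written reaches a sound comparison. Losses before the email should be unrelated to arm. Under the stated follow-up rule non-finishers contribute no outcomes, and the number of starters needed for 180 finishers is the same under either rule. What remains is a preference for strata on survey-measured drinking, worth under 1% in precision once baseline drinking is modelled. Covariates are commonly settled in a statistical analysis plan, which is not shown here.

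This rests on three assumptions: that nothing in the session reveals or acts on the assignment (the protocol describes nothing that does), that the arms are about equal, and that follow-up invitations depend on completed baseline as Study Procedure says. Counting any non-finishers in the participant flow would be ordinary good reporting; it corrects no error in the design.

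### Does the tracking sentence in the warm booster email bias the comparison of warm with automatic boosters?

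*Protocol*

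**What the plan says.** The Description and Purpose section says that online interventions lack a connection with someone who has a stake in how the student does, and that the trial will supply this through a booster sent by research staff. The comparison group will "receive a follow-up booster with similar content, but is clearly automatically generated and not from any particular individual". Both boosters are described there as normative feedback plus feedback on protective strategies. The control email carries no feedback, but it does remind students of the follow-up surveys. Primary Aims asks whether contact from a person adds to the feedback.

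Study Procedure (Baseline) labels the two feedback arms "auto-generated booster email (feedback, no warmth), warm booster email (feedback written by a person using warm, personable language". Study Procedure (Boosters) sets the timing: "Approximately two weeks after the intervention, all participants receive an additional email". It then gives the opening lines of the two boosters:

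- The automatic email says the feedback was generated "based on your answers to the online survey you completed in the research lab for the Project".
- The warm email comes from someone who introduces themselves as "your personal research coordinator for the Project" and adds "I track your responses over the course of the study".

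Outcomes come from online surveys at about 1 and 3 months. Of the reminder that carries the survey link, the protocol says: "This email includes a link to an online follow-up survey that assesses alcohol use, related problems". According to Measures, alcohol use "is assessed using a modified version of the Daily Drinking Questionnaire for the past 30 days".

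**The concern.** Read side by side, the two openings differ in more than tone. The warm email refers to answers still to be given, and the automatic email refers only to the baseline survey. The answers still to be given are the outcomes. A student told that a named person follows their responses might admit to less drinking, or might answer more candidly, with no change in behaviour. Measures lists no biomarker or collateral report, so the analysis could not separate changed reporting from changed drinking. Randomisation gives no protection, because the cue is delivered after assignment. It also falls on the very contrast named in the primary aim. If it mattered, a difference between warm and automatic could be credited to personal contact when it came from reporting, or a real benefit could be hidden.

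**Working it through.** **1. Is the sentence outside the treatment?**

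| Element | Automatic booster | Warm booster | Stated as an intended difference? |
|---|---|---|---|
| Normative feedback | yes | yes | no, common to both |
| Protective-strategies feedback | yes | yes | no, common to both |
| Sender | no individual | named coordinator | yes |
| Tone | neutral | warm, personal | yes |
| Sender follows the student through the study | not in the quoted lines | stated | part of the sender's role |

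The phrase about similar content concerns the first two rows, since both conditions are described as the same two kinds of feedback. It does not promise matching text. The last row is one way of conveying the personal connection that the Description and Purpose section sets out to create. A coordinator who took no interest in later answers would hardly be the invested person described there. If being followed by someone leads a student to drink less, that is an effect of the treatment.

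**2. How different is awareness of follow-up between arms?**

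Eligible students are asked at screening for name, email and phone number (Recruitment Procedure). All are invited to two follow-up surveys, with \$10 for each and a \$10 bonus for completing every assessment (Study Procedure). All receive a two-week email and the 1- and 3-month reminders. The control email itself mentions the coming surveys. The automatic booster uses the recipient's name and own answers. So every arm can tell that identified answers are collected over time. What only the warm arm is told, in the text shown, is that a particular person is doing it, and that is the intended manipulation.

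**3. What would a reporting shift do?**

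The protocol's one power figure (.813 with N = 180) does not depend on email wording. It can be neither confirmed nor faulted here, because alpha, sidedness, the contrast and the covariances are not given. The protocol states no size for a reporting shift, so every shift below is an assumption.

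- Retained per arm: 180/3 × 0.76 = 45.6 (equal allocation assumed).
- Standard error of a difference in SD units: √(2/45.6) = 0.209.
- With baseline adjustment at an assumed correlation of 0.6: 0.209 × √(1 − 0.36) = 0.168.
- With no true effect and a shift d towards less reported drinking in the warm arm: P(significant, favours warm) = P(Z > 1.96 − d/SE). The chance of a significant result against warm is P(Z > 1.96 + d/SE), and the two-sided rate is the sum.

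| Assumed shift (SD) | Favours warm, unadjusted | Against warm, unadjusted | Two-sided, unadjusted | Favours warm, adjusted | Two-sided, adjusted |
|---|---|---|---|---|---|
| 0 | 2.5% | 2.5% | 5.0% | 2.5% | 5.0% |
| 0.05 | 4.3% | 1.4% | 5.7% | 4.8% | 6.0% |
| 0.10 | 6.9% | 0.7% | 7.7% | 8.6% | 9.2% |
| 0.20 | 15.7% | 0.2% | 15.9% | 22.2% | 22.3% |

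If the cue made students more candid, the columns for and against warm would change places: at 0.10 SD the chance of a spurious result favouring warm would fall from 2.5% to 0.7%. The table is the same whatever causes the shift. It does not attribute any of it to the sentence as opposed to the named sender.

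**4. The recall window.**

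With the email at day 14 and the survey at day 30, (30 − 14)/30 = 16/30 = 53% of the 1-month recall period follows the email. This applies equally to both boosters, so it creates no imbalance between them. At 3 months all 30 recalled days follow the email.

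**5. Would changing the wording settle it?**

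Deleting the sentence would alter the intervention and might remove a real accountability effect. A named coordinator commenting on the student's own answers would remain, and could affect reporting too. An impersonal tracking sentence in all three emails would not equalise the cue, because it names nobody, and it would add a monitoring message to the control arm. Each change trades one interpretation for another.

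**The case for a change.** The strongest opposing case is that warmth and a named sender already deliver personal contact, while a statement about tracking is a message about measurement. It could be dropped at almost no cost, and with self-report alone no analysis can separate reporting from behaviour afterwards.

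Much of this stands as fact. The quoted openings do differ, the emails precede both follow-ups, no objective measure of drinking is listed, and the arithmetic is correct. Differential reporting between the two boosters cannot be excluded.

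The step from there to a flaw fails. The claim that the sentence is separable from personal contact is a view about the mechanism, and the protocol's description of the missing ingredient supports the other reading at least as well. The imbalance is also known only from opening lines: the rest of both boosters and the wording of the control email are not shown, so whether other arms are told something similar is unknown. Finally, the reporting worry applies to any trial that compares a human sender with a machine on self-reported outcomes, and it would survive removal of the sentence.

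**Conclusion.** The concern does not hold. The tracking sentence contradicts nothing in the protocol and falls within the personal contact that the trial sets out to test. Whether to word the email differently is a design preference on which reasonable investigators can disagree.

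The possible bias has unknown size and direction. Under assumed shifts of 0.05 to 0.20 SD, 45.6 retained per arm and no true effect, the two-sided false-positive rate would lie between 5.7% and 15.9% unadjusted, or between 6.0% and 22.3% with an assumed baseline correlation of 0.6. Nothing in the documents indicates that this sentence produces a shift of that order. The proper reading of the warm-versus-automatic contrast is the effect of the whole staff-signed email on self-reported drinking and problems. The conclusion rests on the Description and Purpose section's account of the treatment and on the opening lines of the two emails. It would need another look if the protocol had claimed to isolate tone alone.
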